Objectives: Primary objective: 
To evaluate the safety and tolerability of long-term exposure to WVE-120101 in patients with early manifest Huntington's disease (HD) Secondary objectives: 
To evaluate the clinical and pharmacodynamic (PD) effects of WVE-120101 in patients with early manifest HD Exploratory Objectives: 
To evaluate the pharmacokinetics (PK) of WVE-120101 in plasmaTo evaluate WVE-120101 related excretion in urineTo evaluate the exposure of WVE-120101 in cerebrospinal fluid (CSF)To evaluate the effect of WVE-120101 on exploratory biomarkers			
Methodology: This is an open-label extension (OLE) study to evaluate the safety, tolerability, PK, PD, and clinical effects of WVE-120101 in adult patients with early manifest HD who carry a targeted single nucleotide polymorphism, rs362307 (SNP1). The planned duration of this study is approximately 101 weeks. To participate in the study, patients must have completed their Day 168 or 196 visit (depending upon dosing cohort and requirements in a given country) of the Phase 1b/2a clinical study WVE-HDSNP1-001. Screening may last up to 4 weeks. Patients will be dosed on Day 1 with WVE-120101 administered via the intrathecal (IT) route. Patients will return to the clinic every 4 weeks for dosing visits and safety monitoring. Every 12 weeks, patients will undergo assessments of clinical effects. After the last dosing visit (Week 97), patients will return for 1 follow-up safety visit at Week 101. Dose Modifications 
In the original OLE study protocol, patients who were in the 2 and 4 mg dose cohorts in the Phase 1b/2a study were enrolled into the 4 or 8 mg dose group in this study. Patients who were in the 8 and 16 mg dose cohorts in the Phase 1b/2a study were enrolled into the 8 or 16 mg dose groups, respectively in this study. As of this amendment, patients will receive 16 mg or a higher dose of WVE-120101 in this study. The maximum dose and frequency in this OLE study in a given country will not exceed the maximum dose and frequency described in the Phase 1b/2a protocol (WVE-HDSNP1-001) approved in that country. If a dose lower than the maximum dose described in the Phase 1b/2a study is chosen for multiple dosing based on the safety review of the Phase 1b/2a study data by the Dose Escalation Committee (DEC) and Safety Monitoring Committee (SMC), that dose will be used in this OLE study.
 
Based on the SMC and DEC review of Phase 1b/2a safety data, the highest tolerated dose level and/or a lower dose level may be selected for multiple dosing and further evaluation in the OLE. If one dose level is selected, all patients will be switched to receive treatment at that dose level. If more than one dose is selected, patients will be randomized 1:1 to the highest tolerated dose and one lower dose to be determined by the DEC in
			

Sponsor:	Investigational Product:	Developmental Phase:	EudraCT Number:
Wave Life Sciences	WVE-HDSNP1-002	Phase 1b/2a	2019-003637-42

agreement with the SMC. The randomization will be stratified by cohort and use a fixed block size. These doses may be further revised based on emerging safety, PD, or clinical effects data in the Phase 1b/2a study. The maximum dose and frequency in this OLE study will not exceed the maximum dose and frequency described in the Phase 1b/2a protocol (WVE-HDSNP1-001) approved in each country.
 
Dose modification will occur at the next scheduled visit from the date of implementation of this amendment (Amendment 1.0). In addition to the assessments performed at every dosing visit, the Unified Huntington's Disease Rating Scale (UHDRS) and clinical laboratory evaluations should be performed at the visit when a dose is changed.
			

Number of Patients (Planned): Approximately 50 patients will be enrolled.
			

Study Population: Patients must satisfy all of the inclusion and none of the exclusion criteria to be eligible for the study.
			

Inclusion Criteria:
			

 1. Patient has documented ability to understand the written study informed consent forms (ICFs) at the time of screening and has provided signed written informed consent prior to any study procedures. 2. Patient successfully completed their Day 168 or 196 visit (depending upon dosing cohort and requirements in a given country) of the Phase 1b/2a study with WVE-120101, WVE-HDSNP1-001. 3. In the opinion of the Investigator, the patient is able to tolerate all study procedures, is willing to comply with all other protocol requirements, and tolerated study drug in the parent study. 4. Patient is willing to practice highly effective contraception for the duration of the study if the patient or their partner are of childbearing potential. Non-childbearing potential and highly effective methods of contraception are defined in the protocol (Section 5.2.1.1). 			

Exclusion Criteria
			

 1. Clinically significant medical finding on the physical examination other than HD that, in the judgment of the Investigator, will make the patient unsuitable for participation in and/or completion of the study procedures. 2. Received an investigational drug other than WVE-120101, including an investigational oligonucleotide, within the past 1 year or 5 half-lives of the drug, whichever is longer. 3. Implantable central nervous system (CNS) device that may interfere with ability to administer study drug via lumbar puncture or undergo brain magnetic resonance imaging (MRI) scan. 4. Diagnostic and Statistical Manual of Mental Disorders 5th Edition (DSM-5) diagnosis at the Screening Visit of active alcohol, cannabinoid, or other substance use disorder (except nicotine). 5. Positive for opioids (unprescribed), cocaine, amphetamines, methadone, barbiturates, methamphetamine, or phencyclidine at the Screening Visit. 6. Pregnant (as determined by a serum pregnancy test) or breast feeding at the Screening Visit, or plans to become pregnant during the course of the study. 7. Clinically significant laboratory abnormality at Screening, including, but not limited to: 
 a. Alanine aminotransferase (ALT) or aspartate aminotransferase (AST) values at Screening or Baseline >3 times the upper limit of normal (ULN). b. Renal insufficiency, defined as either serum creatinine >1.8 mg/dL or creatinine clearance <40 mL/min. 8. Clinically significant abnormality at Screening electrocardiogram (ECG), including but not limited to a confirmed QT interval corrected for heart rate (QTc) ≥450 msec for males or ≥470 msec for females. 			

Sponsor:	Investigational Product:	Developmental Phase:	EudraCT Number:
Wave Life Sciences	WVE-HDSNP1-002	Phase 1b/2a	2019-003637-42

9. Clinically significant cardiovascular, endocrine, hepatic, renal, pulmonary, gastrointestinal, neurologic, malignant, metabolic, psychiatric, or other condition that, in the opinion of the Investigator, precludes the patient's safe participation in the study or would interfere with the study assessments.
 
10. Bone, spine, bleeding, or other disorder that exposes the patient to risk of injury or unsuccessful lumbar puncture.
 
11. Inability to undergo brain MRI (with or without sedation).
 
12. In the opinion of the Investigator, deemed to be at significant risk for suicidal behavior.
 
13. Involved directly or indirectly in the conduct and administration of this study as an Investigator, sub-investigator, study coordinator, or other study staff member, or the patient is a first-degree family member, significant other, or relative residing with one of the above persons involved directly or indirectly in the study.
 
14. Anticipates using antiplatelet or anticoagulant therapy during the course of the study. Patients who received antiplatelet or anticoagulant therapy must complete one of the following washout periods before the Screening Visit:
 
 A 7-day washout period for antiplatelet therapy, A 1-day washout period for anticoagulants (except warfarin), or A 5-day washout period for warfarin. 			

Investigational Product, Dose, Route, Regimen: WVE-120101. Patients will receive ≥ 16 mg (not to exceed the maximum dose and frequency described in the Phase 1b/2a protocol (WVE-HDSNP1-001) approved in each country). The investigational product will be supplied as a lyophilized powder that will be reconstituted into an injectable solution. The route of administration of the reconstituted WVE-120101 solution will be IT injection by direct lumbar puncture.
			

Reference Therapy, Dose, Route, Regimen: Not applicable. All patients will receive WVE-120101.
			

Study Duration: The planned duration is 101 weeks. Patients will receive doses every 4 weeks over a period of 97 weeks, then complete a safety follow-up phase.
			

Endpoints:
 
Safety Endpoints:
 
The number of patients with adverse events (AEs), severity of AEs, number of patients with serious AEs (SAEs), clinically significant changes in laboratory values, and the number of patients who withdraw due to AEs.
 
Clinical Effects Endpoint(s):
 
 Change from baseline in the Total Functional Capacity (TFC), administered as part of the Unified Huntington's Disease Rating Scale (UHDRS) Change from baseline in the motor, cognitive, independence, and functional assessments administered as part of the UHDRS Change from baseline in the composite UHDRS (cUHDRS) Change from baseline in the Short Problem Behaviors Assessment (PBA-s) 
Pharmacodynamic Endpoints:
 
 Change from baseline in the concentration of mutant huntingtin (mHTT) protein in CSF Changes from baseline MRI of the brain 			

Sponsor: Wave Life Sciences	Investigational Product: WVE-HDSNP1-002	Developmental Phase: Phase 1b/2a	EudraCT Number: 2019-003637-42

• Change from baseline in exploratory biomarkers, including but not limited to neurofilament light (NFL) 
PK Endpoints:
 
• PK parameters of WVE-120101 in plasma• WVE-120101 and WVE-120101-related metabolite excretions in urine• Concentration of WVE-120101 in CSF			

Statistical Methods:
 
Sample size determination
 
No sample size calculations were performed. As this is an OLE, the maximum sample size is fixed by the number of patients completing the WVE-HDSNP1-001 study.
 
Analysis populations
 
The safety population will include all enrolled patients who have received at least one dose of study medication in the OLE. The safety population analysis set will be used for summaries of safety and clinical effects.
 
The per-protocol population will be a subset of the safety population and include patients with no major protocol deviations that will interfere with the assessment of the clinical effects endpoints and with at least 80% compliance to the dosing regimen.
 
The PK population will consist of all patients in the safety population with at least one post-dose plasma or CSF concentration measurement.
 
Analysis of safety
 
The primary objective of this OLE is to evaluate the safety of WVE-120101. The safety analysis will be descriptive and will include summaries of treatment-emergent AEs (TEAEs), TEAEs leading to treatment discontinuation, TEAEs by severity, TEAEs by relationship, and serious TEAEs. Changes in laboratory assessments will also be summarized.
 
Analysis of Clinical Effects and PD
 
The change from baseline for clinical effects and PD endpoints will be summarized using a mixed model for repeated measures (MMRM) with the safety population. The MMRM will be used to construct 95% confidence intervals and to test if the change is statistically significant.
			

TABLE OF CONTENTS

Title Page	1
Clinical Protocol Approval Form	2
Principal Investigator’s Agreement	3
Protocol Synopsis	4
Table of Contents	8
List of Appendices.....	10
List of Tables	10
List of Figures.....	11
List of Abbreviations	12
1 Introduction.....	14
1.1 Disease Background.....	14
1.2 Investigational Product WVE-120101.....	14
1.3 Nonclinical Data	15
1.4 Clinical Experience	16
2 Rationale for the Study	17
2.1 Rationale for the Doses, the Dosing Regimen, and Route of Administration	17
3 Study Objectives	18
4 Study Design.....	19
4.1 Study Design Overview.....	19
4.1.1 Screening Phase.....	20
4.1.2 Treatment Phase	21
4.1.3 Follow-Up Visit.....	22
4.1.4 Early Treatment Withdrawal and Early Termination.....	22
4.2 Schedule of Assessments.....	22
4.3 Study Endpoints	28
4.4 Safety Monitoring Committee Reviews	28
5 Patient Selection and Withdrawal Criteria.....	29
5.1 Inclusion Criteria	29

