In single and repeat-dose IT studies in rats and monkeys, transient, dose-dependent limb dysfunction was observed. In rats findings were observed at dose levels of 0.1 mg (human equivalent dose [HED] 56 mg) in a single-dose study and 0.05 mg (HED 28 mg) and above in repeat doses. These findings resolved within 72 hours. In monkeys, findings were observed at doses up to 6 mg (HED 67.2 mg). Over the course of 9 months in a chronic toxicity study in monkeys, affected animals at doses ≤ 2 mg experienced only 1 or 2 instances of limb dysfunction at sporadic time points. In monkeys, only the lower hind limbs were affected and findings were completely resolved within 48 hours post-dose. Due to their transience, lack of correlating histopathology, and lack of effect on the ability of animals to eat or ambulate, the findings were considered non-adverse.

Microscopic CNS findings were observed in both rats and monkeys after IT administration of WVE-120101. In rats, after 3 months of repeat IT dosing, cellular infiltrates, minimal to mild non-adverse spinal nerve root degeneration, and gliosis were observed. The findings were dose- and/or dose-concentration dependent, with minimal effects observed at 0.05 mg (dose concentration 2 mg/mL). In monkeys, after 3 to 9 months of repeat IT dosing, minimal to mild (3-month study) or minimal to moderate (9-month study) mononuclear cell infiltrates were observed at all doses evaluated. These findings were considered manifestations of the injection procedure and a general response to the immune-stimulating properties of the oligonucleotide^{17,18} and were considered non-adverse.

WVE-120101 demonstrated minimal potential for class effects associated with phosphorothioate oligonucleotides, such as systemic pro-inflammatory effects, activated partial thromboplastin time (aPTT) prolongation, hepatotoxicity, and nephrotoxicity^{18,19}. In addition, WVE-120101 was not associated with any other toxicities, including mutagenicity or effects on cardiovascular or respiratory function, and WVE-120101 exhibited minimal potential for off-target effects via bioinformatic analysis of the human genome.

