1.4 Clinical Experience

WVE-120101 is currently being evaluated in a Phase 1b/2a multicenter, randomized, double-blind, placebo-controlled study to evaluate the safety, tolerability, pharmacokinetics (PK), and

pharmacodynamics (PD) of single and multiple doses of IT WVE-120101 in adult patients with early manifest HD who carry a targeted single SNP, SNP1 (WVE-HDSNP1-001).

In the Phase 1b/2a study, as of the last data cutoff at single doses up to 16 mg (20 March 2020) and multiple doses up to 4 mg (02 March 2020), no stopping criteria have been observed. No related SAEs or related TEAEs associated with the HLTG *Spinal Cord and Nerve Root Disorders* have been reported. No clinically meaningful trends in hematology, coagulation, or chemistry values followed dosing. Final data are not yet available from this study. An independent Safety Monitoring Committee (SMC) will continue to review safety data from study WVE-HDSNP1-001 on an ongoing basis. The SMC will also review data for this OLE study in conjunction to the data from the Phase 1b/2a study to inform decisions in dose escalation and continuation of multiple dosing. If any stopping rules are met in the Phase 1b/2a study, or if the SMC decides to stop the Phase 1b/2a study for any other reason, those decisions will also apply to this study. More detailed information is provided in the Investigator's Brochure.

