Based on the SMC and DEC review of Phase 1b/2a safety data, the highest tolerated dose level and/or a lower dose level may be selected for multiple dosing and further evaluation in the OLE. If one dose level is selected, all patients will be switched to receive treatment at that dose level. If more than one dose is selected, patients will be randomized 1:1 to the highest tolerated dose and one lower dose to be determined by the DEC in agreement with the SMC. The randomization will be stratified by cohort and use a fixed block size. These doses may be further revised based on emerging safety, PD, or clinical effects data in the Phase 1b/2a study. The maximum dose and frequency in this OLE study will not exceed the maximum dose and frequency described in the Phase 1b/2a protocol (WVE-HDSNP1-001) approved in each country. For more details on additional dose modifications refer to [Section 4.1](#).

At the time when the Phase 1b/2a study is completed, the dose and dose interval in this OLE study may be further adjusted. A final determination about the optimal dose and dose-frequency will be made on the basis of data from the WVE-HDSNP1-001 study. It is possible that patients will be up-titrated or down-titrated depending on the dose they were receiving at the time of that decision. Up- or down-titration of the dose will only occur at the cohort level, not on an individual patient level.

The follow-up period will continue to Week 101, 4 weeks after the last dose. Based on PK data from animal studies, the plasma half-life of WVE-120101 is less than 24 hours and the potential for accumulation is low. Clinical data from the ongoing WVE-HDSNP1-001 study show that adverse events tend to occur within the first week or two after dosing. A 4-week follow-up period after the last dose is therefore considered a sufficient period of time to observe potential adverse events.

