9.1 Eliciting and Documenting Adverse Events

All AEs reported or observed during the study, including AEs resulting from concurrent illnesses, reactions to concurrent medications, or progression of disease states, will be recorded on the AE page in the eCRF and in the site source notes. The eCRFs used to document AEs are designed to help ensure this information is collected in a standard way. Information to be collected includes event term, date and time of onset, date and time of resolution, Investigator-specified assessment of severity and relationship to study treatment, action taken with respect to study treatment, seriousness, any required treatment or evaluations, and outcome. All AEs will be followed to adequate resolution. The sites will be provided with completion guidelines for the eCRF, which will further guide them on how to record the data, including AEs.

Any medical condition that is present at the time the patient is screened but does not worsen should not be reported as an AE. However, if it worsens at any time during the study, it should

be recorded as an AE. This includes any spontaneously reported worsening of depression, i.e., not based on the study rating scales.

In addition to observations of the patient, AEs identified from any study data (e.g., laboratory values, physical examination findings, ECG changes) or identified from review of other documents that are considered clinically significant will be documented on the AE page in the eCRF. Worsening of symptoms that are only detected on clinical effects rating scales will not be reported as AEs.

Adverse events will be assessed at each visit by direct questioning as well as elicited from physical examination by site staff. In addition, all sites in the study must ensure patients have a 24-hour telephone number to contact medical site staff for the duration of the study, in case of emergent AEs or SAEs.

If there is any doubt as to whether a clinical observation is an AE, the event should be reported.

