10.4.2 Analysis of Safety Data

The summary of safety results will be presented by dose group. All safety analyses will be performed on the safety population using the following common rules:

- The OLE baseline value is defined generally as the last available value from WVE-HDSNP1-001 before first dose in WVE-HDSNP1-002.
- The repeat dosing baseline value is defined generally as the last available value before initiation of repeat dosing. Initiation of repeat dosing can occur in either WVE-HDSNP1-001 or WVE-HDSNP1-002.
- Adverse event observation periods are defined as follows:
 - Pre-OLE treatment AEs are AEs that developed or worsened between the date of signed informed consent for the OLE and the date of first dose of study drug in the OLE.
 - OLE on-treatment adverse events are AEs that developed or worsened from the first dose of study drug in the OLE to study completion/discontinuation. Summaries of TEAEs will include all OLE on-treatment AEs.
 - Repeat dosing on-treatment adverse events are AEs that developed or worsened from the first dose of repeat dosing to study completion/discontinuation. Initiation of repeat dosing can occur in either WVE-HDSNP1-001 or WVE-HDSNP1-002. Summaries of repeat dosing TEAEs will include all repeat dosing on-treatment AEs.
- For quantitative safety parameters based on central laboratory/reading measurement descriptive statistics will be used to summarize results and change from baseline values by visit and dose group.

Adverse Events

Treatment-emergent AEs, treatment-emergent SAEs, and TEAEs leading to treatment discontinuation will be summarized by dose group based on Medical Dictionary for Regulatory Activities (MedDRA) coding of verbatim terms reported by investigators.

Adverse event incidence tables will present, by system organ class (SOC) and preferred term, the number and percentage of patients experiencing an AE. Multiple occurrences of the same event will be counted once in the tables. The denominator for computation of percentages is the safety population within each dose group.

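### The planned adverse event tables have no time-since-injection or recurrence axis, so on their own they cannot tell brief post-dose motor events from Huntington's disease progression

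*Combined protocol and SAP*

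**What the plan says.** The synopsis (Statistical Methods, Analysis of safety) gives the overall approach: "The safety analysis will be descriptive and will include summaries of treatment-emergent AEs (TEAEs", with breakdowns for discontinuation, severity, relationship and seriousness.

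Section 10.4.2 supplies the detail:

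- Table layout: "Adverse event incidence tables will present, by system organ class (SOC) and preferred term, the number and percentage of patients experiencing an AE", by dose group.
- Counting rule: "Multiple occurrences of the same event will be counted once in the tables".
- Observation window: "OLE on-treatment adverse events are AEs that developed or worsened from the first dose of study drug in the OLE to study completion/discontinuation". A parallel window starts at the first repeat dose in either study.
- Further tables by severity and by relationship, and listings of all adverse events.

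No summary in Section 10.4.2 uses time since the preceding injection, number of episodes or duration. None covers the targeted motor examination that Table 1 schedules at 1 and 4 hours after dosing.

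Elsewhere the protocol gives reasons to look at timing. Section 1.3: "In single and repeat-dose IT studies in rats and monkeys, transient, dose-dependent limb dysfunction was observed", resolving within 72 hours in rats and 48 hours in monkeys. Section 2.1 justifies the length of follow-up by noting that in the parent study "adverse events tend to occur within the first week or two after dosing". Section 9.1 on data collection: "Information to be collected includes event term, date and time of onset, date and time of resolution".

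**The concern.** There is no untreated or placebo group, so a count of limb weakness, gait or sensory events over about two years has nothing to be read against. Section 9.1 asks for events arising from disease progression to be recorded as adverse events. The only carve-out is worsening seen solely on the clinical rating scales. A motor event caused by an injection and one caused by advancing disease can therefore enter the same row of the same table.

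The two should differ in pattern. An acute effect of the kind seen in animals would be short, would follow an injection and could recur. Progression would tend to last and would have no particular relation to injections. A once-per-patient count over one long window keeps neither feature. What is at stake is how interpretable the primary safety summary is for the one neurological effect that the protocol singles out for a dedicated post-dose examination.

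**Working it through.** The plan has no safety sample size, error rate or power statement to reproduce. The check is a reading of Section 10.4.2 against the rest of the protocol, with two small illustrations.

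**1. Which planned output carries timing?**

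| Output | Timing information |
|---|---|
| Incidence by class and preferred term (10.4.2) | None within the on-treatment window |
| Tables by severity (10.4.2) | None |
| Tables by relationship (10.4.2) | Indirect: Table 5 grades use temporal sequence, cessation and re-administration, as judged by an unblinded investigator |
| Listings of all adverse events (10.4.2) | Can show the recorded onset and resolution, case by case |
| 1 h and 4 h targeted examination (Table 1) | Collected; no summary planned in 10.4.2 |

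The information is collected, but no summary uses it.

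**2. Illustration: two different processes, one table cell.** Doses fall at Weeks 1, 5, ..., 97, so the number of doses is (97 − 1)/4 + 1 = 25. With about 50 patients all completing, that is 50 × 25 = 1,250 injections. Let q be the chance of a brief motor event after one injection (an assumption; the documents give no value), independent across doses. The share of patients with at least one event is 1 − (1 − q)^25.

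| q (assumed) | Patients with ≥1 event | Of 50 | Expected episodes (1,250 × q) |
|---|---|---|---|
| 0.5% | 12% | 5.9 | 6.25 |
| 1% | 22% | 11.1 | 12.5 |
| 2% | 40% | 19.8 | 25 |
| 3% | 53% | 26.7 | 37.5 |

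At q = 2% the incidence table shows about 20 of 50 patients. It would show the same if 20 patients each had a single lasting progression event. This demonstrates the ambiguity; it does not estimate any risk.

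**3. Why a formal clustering test is not the remedy.** If background onsets fell evenly over the 28-day cycle, 3/28 = 10.7% would fall within 72 hours of a dose. With 25 events (assumed), seven or more in that window has one-sided probability 1.4%. The even spread is unsafe, however. Adverse events are elicited by questioning and examination at visits (Section 9.1), most of those visits are dosing visits, and the extra motor examinations are on dosing day. If a fraction f of background events is dated to dosing day, the in-window share becomes f + (1 − f) × 3/28:

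| f (assumed) | In-window share | P(7 or more of 25) with no drug effect |
|---|---|---|
| 0 | 10.7% | 1.4% |
| 10% | 19.6% | 21% |
| 20% | 28.6% | 60% |
| 30% | 37.5% | 88% |

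Modest heaping of onset dates is enough to produce a false signal, so the table should be descriptive.

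**4. Denominators.** In an exact 28-day cycle, calendar days 0–3, 4–14 and 15–27 span 4, 11 and 13 days. Most visit windows are ±1 week, and patients who stop treatment may stay in the study (Section 4.1.4), so actual days at risk are needed in place of these nominal figures.

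**The case against.** The strongest reply is that nothing essential is missing. Tables by class and preferred term are standard, and class rows already aggregate related terms. Relationship grades draw on timing, all events are listed, and onset and resolution times are recorded. The synopsis wording does not rule out further tables. The limb effect is an animal finding that Section 1.3 calls non-adverse. For patients, Section 1.4 reports: "No related SAEs or related TEAEs associated with the HLTG" Spinal Cord and Nerve Root Disorders, at single doses up to 16 mg and multiple doses up to 4 mg.

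Most of this stands, and it limits the point. A reader might infer four stronger things that the documents do not support:

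- That the study cannot separate drug effect from progression. Only the summary tables cannot; the data would allow a better summary.
- That there is a known signal in patients. It is known in rats and monkeys only.
- That the extension drops a grouping used in the parent study's analysis. Section 1.4 is a background statement and does not show how the parent study tabulates events.
- That splitting by preferred term is the fault, or that low power to compare single terms between doses shows a defect. No such comparison is planned; safety is descriptive.

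What the reply does not remove is that relationship grading is unblinded and weakest where the disease mimics the effect, and that a listing is not a pre-specified summary.

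**Conclusion.** The point holds as a cheap improvement to Section 10.4.2. In an uncontrolled study with safety as the primary objective, the planned incidence tables discard time since injection, recurrence and duration, although the protocol itself describes a transient dose-related limb effect in animals and early clustering of events after dosing in patients.

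This rests on the text of Sections 1.3, 2.1, 9.1 and 10.4.2, and on no assumed rate. The documents give no basis for a numerical size. The event counts, per-injection risks and heaping fractions above are assumptions used to show the ambiguity and the limits of a test, and are not evidence of a defect.

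**What to change.** Add one pre-specified descriptive table to Section 10.4.2:

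- **Terms:** a group fixed before database lock, made up of the high-level group term Spinal Cord and Nerve Root Disorders plus a list of limb weakness, gait and sensory terms.
- **Layout:** patients and episodes, by dose given at the preceding injection and by days since it (0–3, 4–14, 15 or more), with duration and days at risk. Using the preceding dose also settles where events belong after a mid-study dose change, which Section 10.4.2 leaves open.
- **Examination findings:** show events found only at the scheduled 1 h and 4 h examinations separately, so that scheduled detection does not swell the early window.
- **Any early-to-late rate ratio:** descriptive only, with an interval that allows for repeat events within a patient.

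The plan should state three limits. Onset dates can heap on dosing days because events are elicited there. An early excess also contains lumbar-puncture effects. It can be read against a concurrent randomised dose comparison only if two dose levels are selected (Section 4.1).

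The cost is one table and an agreed term list. No new data, visits or procedures are needed.
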